The number of participants was calculated using R 4.0 software, as detailed below: Trial Size: Two Sample Proportion. NIS (alpha = 0.05, beta = 0.2, p1 = 0.667, p2 = 0.281, k = 1, delta = 0.386, margin = 0.205) = 80.043° 81 por Grupo.

Number of participants	Sample Size	Drop-out (10%)
162 being:	180	18
81 Placebo group	90 Placebo group	
81 Azvudine group	90 Azvudine group	

"The required sample size for the IGZ-1 protocol is 180 participants, with 90 participants in each group, considering the 10% chance of drop-outs (participants who leave the study for some reason other than its termination)."

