	 Total time of use of AZVUDINE (FNC); 			
	 Proportion of participants who withdrew 			
	consent;			
	 Proportion of participants who dropped out 			
	of treatment.			
	All statistical tests are performed by two-sided test. A			
ANALYSES	significance level of 5% will be adopted. Detailed statistical			
	methods will be provided in chapter 11.			
	From the approval of the study by the Research Ethics			
LENGTH OF STUDY	Committee and ANVISA, it is estimated to take			
	approximately 7 months to complete.			

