11. STATISTICAL ANALYSIS

11.1. SAMPLE SIZE ESTIMATION

This study is a randomized, parallel, double-blind, PLACEBO-controlled clinical trial, with the primary endpoint being the "Proportion of participants with improvement in clinical status [Period: until D15, approximately 14 days]".

This is a randomized, parallel, double-blind, PLACEBO-controlled clinical trial, which after initial study data, the sample size calculation was revised by updating parameters of frequency of clinical improvement and dropout rate. The revised sample size is 180 participants randomly and equally divided into the two arms of the study (90 practitioners in each group).

- Proportion of participants (%) with improvement of clinical status [Period: until
 D15, approximately 14 days].
- Clinical improvement time (median, in days) taking into account the following **PARAMETERS:**

0	Level of Significance	α = 5%
0	Statistical test power	Not less than 80%;
0	Distribution into groups	1:1 ratio
0	Frequency of clinical improvement	p1 = 66.7% in the test
		group;
		p2 = 28.1% in the control
		group
0	Superior efficacy study in terms of	15% established in previous
	frequency of clinical improvement	studies;
0	Median time to clinical	5 days in the test group;
	improvement	7 days in the control group.
0	Minimum detectable HR risk rate	0,7
	over time for clinical improvement	

We use the results of the open-label, randomized, controlled trial report on the efficacy of AZVUDINE 1 mg tablets in the treatment of patients with COVID-19 (HOPE-1) ¹⁸, as reported below:

 The study included male/female patients 18 years and older with a mild course of COVID-19 who received treatment for COVID-19 ("treated") prior to enrollment in the study and, patients who did not receive treatment ("newly diagnosed"). All patients received AZVUDINE at a dose of 5 mg per day for 7 days;

- Analysis of this clinical trial shows that at the start of treatment, 100% of patients tested positive for SARS-CoV-2 RNA, 80% of patients had abnormalities on lung CT, and, 50% of patients had respiratory symptoms and signs.
- According to the WHO COVID-19 Ordinal Scale of Clinical Improvement, 50% of the patients were in category 1 and 50% were in category 2.

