11.3. METHOD OF STATISTICAL ANALYSIS

All statistical tests will be two-sided tests.

- If the p-value is ≤0.05, it is considered that there is statistical significance in the test (unless otherwise specified).
- The quantitative indices describe the mean value, standard deviation, median, minimum value, maximum value, lower quartile (Q1), upper quartile (Q3) to be calculated, and the rank indices describe the frequency and percentage of cases.
- Comparison of the two groups under general conditions will be analyzed with appropriate methods according to the types of indicators. Student's ttest or Mann-Whitney test will be used to compare the groups for quantitative data. Chi-square test or Fisher's exact test will be used for categorical data.
- The selected cases should be grouped and at the end of the study determine the three analysis data sets (FAS, PPS, SS).
- For the analysis of demographic information and baseline eigenvalues, the mean value, standard deviation, quartiles, minimum value and maximum value should be calculated for numeric variables. For categorical data, frequency and percentage will be calculated.
- For analysis of medication and drug combination adherence one should calculate the percentage of individuals whose medication adherence is at

least 80-100%. An analysis of the classification of the combination of drugs should also be done.

• For analysis of the primary effectiveness indicator:

Primary Goal

To evaluate the **efficacy and safety of** AZVUDINE (FNC) versus placebo in patients infected with moderate to severe stage SARS-COV-2;

Analysis method:

For the efficacy analysis a logistic regression model will be used with the dependent variable "The proportion of participants with clinical improvement [Period: until D15, approximately 14 days]" and independent variables allocation group, AZVUDINE (FNC) or PLACEBO. For the Safety analysis a logistic regression model will be used with the dependent variable "occurrence of serious adverse events" and independent variables allocation group, AZVUDINE (FNC) or PLACEBO. As a support analysis, with exploratory character, both for efficacy and safety, covariate models will be built as well as other variables that present, in the univariate analysis, statistical significance.

Secondary objective

To evaluate the **clinical outcome** between the AZVUDINE (FNC) group versus placebo in patients infected with moderate to severe stage SARS-COV-2;

Analysis method:

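### The 81 per group in section 11.1 is sized for a one-sided 5% test against a 20.5-point margin, which matches neither the two-sided tests, nor the 15% superiority figure, nor the margin-free analysis that the protocol states

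*Protocol*

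**What the plan says.** Protocol section 11.1 names the R routine "Trial Size: Two Sample Proportion. NIS" and its inputs, "alpha = 0.05, beta = 0.2, p1 = 0.667, p2 = 0.281, k = 1, delta = 0.386, margin = 0.205". The result is 80.043, rounded to 81 per group (162), then raised to 90 per group (180) for 10% dropout. No source is given for the 0.205.

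The parameter list earlier in 11.1 gives a 5% significance level without stating sidedness. It asks for power of "Not less than 80" per cent, rates of 66.7% and 28.1%, and, in the row on superior efficacy in frequency of improvement, "15% established in previous" studies. It also gives median times to improvement of 5 days (test) and 7 days (control), and a row "Minimum detectable HR risk rate" with the value 0.7.

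On the analysis, the synopsis (1.1) says "All statistical tests are performed by two-sided test" with a 5% level, and section 11.3 says "All statistical tests will be two-sided tests" with significance at p ≤ 0.05. Section 11.3 analyses the primary endpoint by logistic regression on allocation group. Its table of methods lists a t-test or Mann-Whitney test for the same endpoint. Neither entry mentions a margin.

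**The concern.** A sample-size statement should describe the test that will be run. Here the printed inputs, the parameter list and the analysis section imply three different thresholds for the difference in improvement: above 0, above 15 points and above 20.5 points. They also imply two different uses of the 5%.

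The reading matters for the primary claim. A result whose lower confidence limit for the difference lay at 17 points would succeed under the first two thresholds and fail under the third. With all three in the document, the choice could be argued after the data are known.

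The hazard ratio row makes a second power claim next to the first, and nothing in the document shows that the planned number supports it.

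**Working it through.** **Inputs** (all from Protocol 11.1): p1 = 0.667, p2 = 0.281, power 80%, α = 5%, δ = 0.386, margin 0.205 in the calculation, 15% in the parameter list, 10% dropout.

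**Formula:** n per group = (z_α + z_β)² [p1(1−p1) + p2(1−p2)] / (δ − margin)².

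- Variance sum: 0.667 × 0.333 + 0.281 × 0.719 = 0.2221 + 0.2020 = 0.4241.
- One-sided 5%: (1.645 + 0.842)² = 6.183. Two-sided 5%: (1.960 + 0.842)² = 7.849.

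**Reproducing the protocol's figure.** With margin 0.205, (0.386 − 0.205)² = 0.03276. One-sided, 6.183 × 0.4241 / 0.03276 = 80.04, so 81 per group and 81/0.9 = 90 with dropout. This is the printed result. Two-sided, 7.849 × 0.4241 / 0.03276 = 101.6, which is not.

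**All combinations at the stated rates:**

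| Margin | n per group, one-sided 5% | n per group, two-sided 5% | Power with 81 per group, two-sided 5% |
|---|---|---|---|
| 20.5 points | 80.04 | 101.6 | 70.6% |
| 15 points | 47.1 | 59.8 | 90.3% |
| 0 | 17.6 | 22.3 | above 99.9% |

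The power column is Φ((δ − margin)/√(0.4241/81) − 1.96), where √(0.4241/81) = 0.0724. For 20.5 points this is Φ(0.181/0.0724 − 1.96) = Φ(0.54) = 70.6%. With no dropout at all (90 per group) it is 75.1%. The zero-difference result is 99.96% with unpooled variance and 99.93% with pooled variance.

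The listed 15% therefore gives 81 under neither sidedness. The zero-difference test needs far fewer than 81 at these rates.

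**Hazard ratio 0.7.** Schoenfeld's formula for 1:1 allocation is events = 4(z_α + z_β)²/(ln HR)², with (ln 0.7)² = 0.1272.

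- Two-sided: 4 × 7.849/0.1272 = 246.8, so 247 events.
- One-sided: 4 × 6.183/0.1272 = 194.4, so 195 events.
- Both exceed 180 participants, each of whom can contribute at most one first improvement.

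Two-sided power is Φ(√(events/4) × 0.3567 − 1.96):

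- 180 events (everyone randomised improves): 66.7%.
- 162 events (everyone evaluable improves): 62.2%.
- About 77 events, from 81 × (0.667 + 0.281) = 76.8 at the stated rates: 34.6%.

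**Direction of the hazard ratio.** The medians give 5/7 = 0.71 if the ratio is control over test, and 7/5 = 1.4 if it is test over control (constant hazards assumed). The protocol does not say which is meant.

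**The case against.** The strongest reply is that the planned test has ample power. The analysis in 11.3 is a group effect judged at two-sided p ≤ 0.05. At the protocol's own rates 81 per group gives it more than 99.9% power, so the promise of at least 80% is kept for that test. This stands. A reader might infer from the 70.6% that the trial is underpowered, but that figure belongs to a two-sided margin test that the protocol never schedules.

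Three further limits also stand:

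- The 15% row is not labelled a margin. It is, however, the only superiority figure in the list, and it differs from the 0.205 used.
- One-sidedness is inferred, since the protocol prints only alpha = 0.05. The inference is firm, because only z(0.95) returns 80.04.
- The hazard ratio drives no calculation. Time to clinical improvement on the WHO scale is not among the outcomes in section 4, and 11.3 plans no log-rank or Cox analysis of it. A reader might take 0.7 to mean that azvudine slows improvement. The documents do not support that, because 0.7 agrees with the medians if read as control over test.

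None of this removes the conflict among the printed figures. It limits the consequence to a mismatched justification and an undefined success criterion.

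**Conclusion.** The point holds as an internal contradiction in the sample-size basis, not as a shortage of participants. The 81 per group is the answer to a one-sided 5% test against 20.5 points. The protocol elsewhere states two-sided 5% tests, a 15% superiority figure and a primary model with no margin. Which difference counts as success is therefore not settled.

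If the 20.5-point margin were tested two-sided at 5%, power would be about 71%. Holding 80% would need 102 per group, or 114 per group (228 in total) with 10% dropout. The claim of at least 80% power for a hazard ratio of 0.7 cannot be met under either sidedness, even if all 180 participants improve. The 62% figure should not be taken as its power, since it requires every one of the 162 evaluable participants to improve; the stated rates imply about 35%.

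These results rest on the normal-approximation formulas above and on the protocol's rates of 66.7% and 28.1%. The figure above 99.9% depends on those rates in particular.

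**What to change.** Keep 180 and rewrite 11.1 around one hypothesis: two-sided 5%, null difference 0, matching the logistic model. Remove the 15% and 20.5-point figures. State what 81 per group delivers: roughly 80% power (79 to 82%, depending on whether the variance is pooled) for 28% versus 49%, 50% versus 71%, 60% versus 80%, or 70% versus 88%. Delete the hazard ratio line, since no analysis uses it.

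If a margin is really intended, name one. Make the primary test a comparison of the lower two-sided 95% confidence limit for the difference with that margin, and restate the power at 81 per group: about 71% at 20.5 points or about 90% at 15 points.

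The cost is a rewording of 11.1 and, if a margin is kept, a matching change in 11.3. Enrolment stays the same under the zero-difference option. Keeping the 20.5-point margin means either accepting the less favourable 71% or enrolling 228.

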11.2. STATISTICAL ANALYSIS POPULATION

- Full Analysis Set (FAS): a set of patients who were randomized and received at least one oral dose of the study drug.
- Per protocol set (PPS): a set of data generated by a subset of clinical trial subjects whose protocol compliance was strict, with no significant

deviation from the trial protocol, to ensure that the data are statistically relevant to answer the primary endpoint. PPS analysis will be used for the primary efficacy indicator.

 Safety data set (SS): a set of participants who have received at least one treatment, and have actual data recorded by the safety index after treatment. The SS analysis will be used for the incidence of adverse reactions.

11.3. METHOD OF STATISTICAL ANALYSIS

All statistical tests will be two-sided tests.

- If the p-value is ≤0.05, it is considered that there is statistical significance in the test (unless otherwise specified).
- The quantitative indices describe the mean value, standard deviation, median, minimum value, maximum value, lower quartile (Q1), upper quartile (Q3) to be calculated, and the rank indices describe the frequency and percentage of cases.
- Comparison of the two groups under general conditions will be analyzed with appropriate methods according to the types of indicators. Student's ttest or Mann-Whitney test will be used to compare the groups for quantitative data. Chi-square test or Fisher's exact test will be used for categorical data.
- The selected cases should be grouped and at the end of the study determine the three analysis data sets (FAS, PPS, SS).
- For the analysis of demographic information and baseline eigenvalues, the mean value, standard deviation, quartiles, minimum value and maximum value should be calculated for numeric variables. For categorical data, frequency and percentage will be calculated.
- For analysis of medication and drug combination adherence one should calculate the percentage of individuals whose medication adherence is at

least 80-100%. An analysis of the classification of the combination of drugs should also be done.

• For analysis of the primary effectiveness indicator:

Primary Goal

To evaluate the **efficacy and safety of** AZVUDINE (FNC) versus placebo in patients infected with moderate to severe stage SARS-COV-2;

Analysis method:

For the efficacy analysis a logistic regression model will be used with the dependent variable "The proportion of participants with clinical improvement [Period: until D15, approximately 14 days]" and independent variables allocation group, AZVUDINE (FNC) or PLACEBO. For the Safety analysis a logistic regression model will be used with the dependent variable "occurrence of serious adverse events" and independent variables allocation group, AZVUDINE (FNC) or PLACEBO. As a support analysis, with exploratory character, both for efficacy and safety, covariate models will be built as well as other variables that present, in the univariate analysis, statistical significance.

Secondary objective

To evaluate the **clinical outcome** between the AZVUDINE (FNC) group versus placebo in patients infected with moderate to severe stage SARS-COV-2;

Analysis method:

Univariate analysis of the clinical outcome variables and with the group variable.

- For the secondary efficacy indicator analysis, the coronavirus viral load changes compared to baseline should be calculated for the experimental and control groups separately, as well as the value of the difference between the viral load changes compared to baseline for both groups. The ANCOVA model will be used to estimate the impact of treatment on viral load changes adjusting for other study variables such as disease severity, age, weight, and comorbidities, etc.
 - For analysis of the secondary efficacy indicator one should stratify according to the severity of the disease (severe, severe), following the following statistical methods:

PRIMARY ENDPOINT			ANALYSIS METHOD
•	Propo	rtion of participants with clinical status	Teste t de
	impro	vement [Period: until D15,	Student/Teste de
	appro	ximately 14 days].	Mann-Whitney
	0	The criterion for a participant to have	
		an improvement in clinical status is a	
		decrease on the WHO Clinical	
		Improvement Ordinal Scale in at least	
		one category compared to screening	
		(WHO, Jun/2020).	

SEC	CONDARY OUTCOMES	
•	Proportion of participants with a clinical	Pearson's Chi-
	outcome of cure during the study; [Period:	square test
	until D15, D21, and D28, approximately 14-	
	30 days].	

;	inic	al Trial Design	
		o The clinical endpoint of cure is	Student's t-test /
		defined in this protocol as the	Mann-Whitney
		absence of viral RNA in	test
		collected samples and clinical	
		conditions for	
		hospital discharge.	
	•	Time to normalization of body temperature	Student's t-test /
		(below 37.6c, axillary); [Period: until D15,	Mann-Whitney
		D21 and D28, approximately 14-30 days].	test
		Time to improvement of diarrhea,	Student's t-test /
		myalgia, fatigue, malaise, cough and	Mann-Whitney
		headache; [Period: until D15, D21 and	test
		D28, approximately 14-30 days].	
		Changes in liver and kidney function	Student's t-test /
		baselines, and inflammatory and	Mann-Whitney
		immunological markers: [Period: until	test
		D15, D21 and D28, approximately 14-30	
		days]	
		 Lab tests performed on days D1, 	
		D3, D5, D7, D9, D13, D15, D21,	
		D28, and D60.	
		Evaluation of the time to negative	Student's t-test /
		conversion of SARS-CoV-2 viral load by	Mann-Whitney
		RT-PCR between AZVUDINE (FNC) group	test
		and placebo- control group; [Period: until	
		D15, D21 and D28, approximately 14-30	
		days].	

- Evaluation of the number of cycles for the detection of SARS-CoV-2 viral load byRT-PCR and application of the standard curve for viral load calculation; [Period: until D15, D21 and D28, approximately 14-30 days].
- Student's t-test /
 Mann-Whitney
 test
- Analysis of the relationship between the calculated viral load and the clinical outcome of participants in the AZVUDINE (FNC) group versus the placebo control group; [Period: until D15, D21 and D28,

Generalized linearregression model

- approximately 14-30 days].
- Time and proportion of lung imaging improvement during treatment (Pattern of ground-glass opacities, mosaic paving, alveolar consolidation, reticular pattern/septal thickening, opacity with inverted halo, pleural/pericardial effusion, fibrosis and/or lymphadenomegaly); [Period: until D15, D21 and D28, approximately 14-30 days].

Student's t-test /
Mann-Whitney test
/ Pearson's chisquare test

 Time of improvement and proportion of respiratory symptoms and signs during treatment (Lung rales, cough, sputum, sore throat); [Period: until D15, D21, and D28, approximately 14-30 days].

Student's t-test /
Mann-Whitney test
/ Pearson's chisquare test

·IIIIIC	ai Illai Desigli	
•	Time to normalization of _{O2} saturation (above 95%); [Period: until D15, D21 and D28, approximately 14-30 days].	Student's t-test / Mann-Whitney test
•	Time to normalization of respiratory rate to levels ≤ 24rpm, in room air; [Period: until D15, D21 and D28, approximately 14-30 days]	Student's t-test / Mann-Whitney test
•	Frequency of supplemental oxygenation or non-invasive ventilation; [Period: until D15, D21 and D28, approximately 14-30 days].	Student's t-test / Mann-Whitney test / Pearson's chi- square test
•	Frequency of invasive mechanical ventilation or extracorporeal membrane oxygenation (ECMO); [Period: until D15, D21 and D28, approximately 14-30 days].	Student's t-test / Mann-Whitney test
•	Proportion of moderate cases that progressed to severe cases requiring intensive care unit (ICU) care; [Period: until D15, D21, and D28, approximately 14-30 days].	Pearson's Chi- square test
•	Length of hospital stay; [Period: until D15, D21 and D28, approximately 14-30 days].	Student's t-test / Mann-Whitney test

Jinicai Triai Design	
 Occurrence of drug interactions; [Period: until D15, D21 and D28, approximately 14- 30 days]. 	Pearson's Chi- square test
 Frequency and intensity of adverse events; [Period: until D15, D21 and D28, approximately 14-30 days]. 	Student's t-test / Mann-Whitney test / Pearson's chi- square test
 Frequency and intensity of unexpected adverse events; [Period: until D15, D21 and D28, approximately 14-30 days]. 	Student's t-test / Mann-Whitney test / Pearson's chi- square test
 Frequency and intensity of serious adverse events; [Period: until D15, D21 and D28, approximately 14-30 days]. 	Student's t-test / Mann-Whitney test / Pearson's chi- square test
 All-cause mortality rate during the study; [Period: until D15, D21 and D28, approximately 14-30 days]. 	Mann-Whitnoy tost

Evaluate the tolerability of AZVUDINE (FNC)
 use at 5mg/day regimen for up to 14 days:
 [Period: until D15, approximately 14 days].

 Calculating treatment adherence;
 Total time of use of AZVUDINE
 (FNC);
 Proportion of participants who withdrew consent;
 Proportion of participants who dropped out of treatment.

Student's t-test /
Mann-Whitney test /
Pearson's chi-square test

For safety analysis, AEs should be coded according to the MedDRA terminology dictionary (version 23.0) and the following criteria should be listed and analyzed:

- o Cases of EAs, EAGs, and of EAs leading to abandonment.
- Number and the rate of "normal to abnormal" or "abnormal worsening" of the laboratory and ECG indicator after the experiment.
- Laboratory indicator, ECG, abnormal physical examination cases and clinical interpretation.

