	4) Loss of contact with the participant for follow-up;			
	5) Death;			
	6) Hospital discharge (2 negative RT-PCR tests).			
	The following criteria define the interruption of thestudy			
	as a whole:			
	1) Termination of the trial by the sponsor, if justified;			
	2) Termination of the study by the Principal			
	Investigator, if justified;			
	3) Termination of the study at the request of local			
	ethical and health authorities.			
	Demographic data collection, physical examination, vital			
	signs assessment, blood sampling, respiratory tract			
PROCEDURES	sampling, imaging, ECG, and pregnancy testing (female			
	participants) will be performed			
OUTCOME/ENDPOINTS	PRIMARY ENDPOINT			

- Proportion of participants with clinical status improvement [Period: until D15, approximately 14 days].
 - The criterion for a participant to have an improvement in clinical status is a decrease on the WHO Clinical Improvement Ordinal Scale in at least one category compared to screening (WHO, Jun/2020).

SECONDARY ENDPOINT

- Proportion of participants with a clinical outcome of cure during the study; [Period: until D15, D21, and D28, approximately 14-30 days].
 - The clinical endpoint of cure is defined in this protocol as the absence of viral RNA in collected samples and clinical conditions for hospital discharge³.
- Time to normalization of body temperature (below 37.6°C axillary); [Period: until D15, D21 and D28, approximately 14-30 days]
- Time to improvement of diarrhea, myalgia, fatigue, malaise, cough, dyspnea, and headache; [Period: until D15, D21, and D28, approximately 14-30 days].

³ According to the WHO Working Group on Characterization and Clinical Management of COVID-19 Infection (July, 2020), clinical and virological absence of infection (non-detectable RT-PCR) is suggestive of CURE for initially infected participants.

- Changes in liver and kidney function baselines, and inflammatory and immunological markers: [Period: until D15, D21 and D28, approximately 14-30 days]
 - Lab tests performed on days D1, D3, D5, D7,
 D9, D13, D15, D21, D28, and D60.
- Evaluation of the time to negative conversion of the SARS-CoV-2 viral load by RT-PCR between AZVUDINE (FNC) group and control group; [Period: until D15, D21 and D28, approximately 14-30 days].

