- Time and proportion of lung imaging improvement during treatment (Pattern of ground-glass opacities, mosaic paving, alveolar consolidation, reticular pattern/septal thickening, opacity with inverted halo, pleural/pericardial effusion, fibrosis and/or lymphadenomegaly); [Period: until D15, D21 and D28, approximately 14-30 days].
- Time of improvement and proportion of respiratory symptoms and signs during treatment (Lung rales, cough, sputum, sore throat); [Period: until D15, D21, and D28, approximately 14-30 days].
- Time to normalization of O2 saturation (above 95%);
 [Period: until D15, D21 and D28, approximately 14-30 days].
- Time to normalization of respiratory rate to levels ≤ 24rpm, in room air; [Period: until D15, D21 and D28, approximately 14-30 days]
- Frequency of supplemental oxygenation or non-invasive ventilation; [Period: until D15, D21 and D28, approximately 14-30 days].
- Frequency of invasive mechanical ventilation or extracorporeal membrane oxygenation (ECMO); [Period: until D15, D21, and D28, approximately 14-30 days].

- Proportion of moderate cases that progressed to severe cases requiring intensive care unit (ICU) care; [Period: until D15, D21, and D28, approximately 14-30 days].
- Length of hospital stay; [Period: until D15, D21 and D28, approximately 14-30 days].
- Occurrence of drug interactions; [Period: until D15, D21 and D28, approximately 14-30 days].
- Frequency and intensity of adverse events; [Period: until D15, D21 and D28, approximately 14-30 days].
- Frequency and intensity of unexpected adverse events;
 [Period: until D15, D21 and D28, approximately 14-30 days].
- Frequency and intensity of serious adverse events;
 [Period: until D15, D21 and D28, approximately 14-30 days].
- All-cause mortality rate during the study; [Period: until D15, D21 and D28, approximately 14-30 days].
- Evaluate the tolerability of AZVUDINE (FNC) use at 5mg/day regimen for up to 14 days: [Period: until D15, approximately 14 days].
 - Calculating treatment adherence;
 - Total time of use of AZVUDINE (FNC);
 - Proportion of participants who withdrew consent;
 - Proportion of participants who dropped out of treatment.

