7.1.2. Secondary Efficacy Evaluation (Endpoints)

- Proportion of participants with a clinical outcome of cure during the study; [Period: until D15, D21, and D28, approximately 14-30 days].
 - $_{\odot}$ The clinical endpoint of cure is defined in this protocol as the absence of viral RNA in collected samples and clinical conditions for hospital discharge¹⁴.
- Time to normalization of body temperature (below 37.6°C axillary); [Period: until D15, D21 and D28, approximately 14-30 days]
- Tempo de melhora da diarréia, mialgia, fadiga, mal-estar, tosse, dispnéia e cefaléia;
 [Período: até o D15, D21 e D28, aproximadamente 14-30 dias]
- Changes in liver and kidney function baselines, and inflammatory and immunological markers: [Period: until D15, D21 and D28, approximately 14-30 days]
 - Lab tests performed on days D1, D3, D5, D7, D9, D13, D15, D21, D28, and
 D60.
- Evaluation of the time to negative conversion of the SARS-CoV-2 viral load by RT-PCR between AZVUDINE (FNC) group and control group; [Period: until D15, D21 and D28, approximately 14-30 days].
- Evaluation of the number of cycles for the detection of SARS-CoV-2 viral load by RT-PCR and application of the standard curve for viral load calculation; [Period: until D15, D21 and D28, approximately 14-30 days].

¹⁴ According to the WHO Working Group on Characterization and Clinical Management of COVID-19 Infection (July, 2020), clinical and virological absence of infection (non-detectable RT-PCR) is suggestive of CURE for initially infected participants.

- Analysis of the relationship between the calculated viral load and the clinical progress of participants in the AZVUDINE (FNC) group compared to the control group; [Period: until D15, D21 and D28, approximately 14-30 days].
- Time and proportion of lung imaging improvement during treatment (Pattern of ground-glass opacities, mosaic paving, alveolar consolidation, reticular pattern/septal thickening, opacity with inverted halo, pleural/pericardial effusion,

fibrosis and/or lymphadenomegaly); [Period: until D15, D21 and D28, approximately 14-30 days].

- Time of improvement and proportion of respiratory symptoms and signs during treatment (Lung rales, cough, sputum, sore throat); [Period: until D15, D21, and D28, approximately 14-30 days].
- Time to normalization of ₀₂ saturation (above 95%); [Period: until D15, D21 and D28, approximately 14-30 days].

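### The unadjusted p≤0.05 rule covers 21 secondary outcomes with no main window named, so a false significant secondary result is about as likely as not, or more likely

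*Protocol*

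**What the plan says.** The synopsis states that a "significance level of 5% will be adopted", and section 11.3 that "All statistical tests will be two-sided tests". Section 11.3 then defines significance for all tests: "If the p-value is ≤0.05, it is considered that there is statistical significance in the test (unless otherwise specified"). Nothing different is specified for any secondary outcome.

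The secondary outcomes are listed in the synopsis, section 4 and section 7.1.2, and again in the method table of section 11.3. Each list has 21 entries. Twenty carry three windows, for example "Time to normalization of body temperature (below 37.6°C axillary); [Period: until D15, D21 and D28, approximately 14-30 days" and "All-cause mortality rate during the study; [Period: until D15, D21 and D28, approximately 14-30 days". The exception is tolerability, at the "5mg/day regimen for up to 14 days: [Period: until D15, approximately 14 days", which has four sub-items.

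The secondary objective is to be answered by "Univariate analysis of the clinical outcome variables and with the group variable", and the method table assigns a test or model to each entry. No order, key secondary endpoint, main window or multiplicity adjustment is given. The label exploratory appears in section 11.3 only for the covariate models that support the primary analyses.

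**The concern.** Taken as written, any of 21 secondary comparisons may be reported as statistically significant at 5%, and for 20 of them the window is left open. A drug with no effect on these outcomes would then have a much larger than 5% chance of yielding at least one significant secondary finding. For a single endpoint, the most favourable of three windows could be quoted. The secondary objective concerns clinical outcome in general, so readers could not tell a real secondary effect from one expected by chance.

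**Working it through.** The protocol states no overall error rate for the secondary outcomes; its only figure is 5% per test. There is thus no figure of its own to reproduce.

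**Inputs.** From the protocol: two-sided α = 0.05 per test; 21 secondary outcomes; 20 with three windows and one with a single window. Assumed, because the protocol does not give them: no true effect on any secondary outcome; correlation rb between outcomes of 0 to 0.5; correlation rw between windows of one outcome of 0.5 to 0.95.

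**One test per outcome, independent.** 1 − 0.95^21 = 65.9%. Expected false positives: 21 × 0.05 = 1.05.

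**Every window tested, independent.** 20 × 3 + 1 = 61 tests give 1 − 0.95^61 = 95.6%, with 61 × 0.05 = 3.05 expected. Counting the four tolerability sub-items separately gives 20 × 3 + 4 = 64 tests, 1 − 0.95^64 = 96.2%, with 3.2 expected. The expected counts hold under any correlation; the probabilities do not.

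**Allowing for correlation.** Each z-statistic was simulated as √rb·g + √(rw−rb)·o + √(1−rw)·e, where g is shared by all outcomes, o by the windows of one outcome, and e is specific to the test. There were 200,000 runs, and a test was significant if |z| > 1.96. Chance of at least one false positive:

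| rb | One window (21 tests) | 61 tests, rw 0.5 | rw 0.7 | rw 0.9 | rw 0.95 |
|---|---|---|---|---|---|
| 0 | 66.1% | 93.5% | 90.5% | 83.4% | 79.4% |
| 0.2 | 60.6% | 89.3% | 86.1% | 78.4% | 73.9% |
| 0.3 | 55.6% | 84.1% | 81.1% | 73.3% | 68.7% |
| 0.5 | 43.0% | 66.8% | 64.8% | 58.3% | 54.5% |

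High rw is plausible because the windows are cumulative. Note 5 to Table 10 also restricts the D21 procedures to participants still in hospital.

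**Best of three windows for one endpoint.** A simulation of 20,000 draws gives 12.5%, 10.9% and 8.4% for rw of 0.5, 0.7 and 0.9, against a nominal 5%.

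**Direction.** With two-sided tests, a false result favours the drug with probability 0.025. Setting aside six entries that are wholly or partly safety or tolerability (laboratory markers, drug interactions, three adverse-event entries, tolerability) leaves 15.
- One test each: 15 × 0.025 = 0.4 false benefits expected; 1 − 0.975^15 = 32% chance of at least one if independent.
- Three windows each: 45 × 0.025 = 1.1 expected; 1 − 0.975^45 = 68% if independent.

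**What the counts leave out.** Some entries hold several measures, such as "Time to improvement of diarrhea, myalgia, fatigue, malaise, cough, dyspnea, and headache" with seven. A rough split into 40 components × 3 windows + 1 = 121 tests, at rw 0.9, gives 97.1%, 93.9%, 90.0% and 74.3% for rb of 0, 0.2, 0.3 and 0.5. Separate component tests are a further assumption.

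**The case against.** The strongest reply is that multiplicity belongs to the statistical analysis plan. Section 5.4.4 makes a final statistical plan a condition of unblinding, and the rule in section 11.3 allows exceptions. A missing hierarchy alone would indeed be no finding. But the protocol states what counts as significant for every test, and that sentence permits unadjusted claims unless it is narrowed.

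A second reply is that secondary outcomes are supportive by label and the sentence sets no rule for declaring efficacy. This is fair as far as it goes: a single primary efficacy endpoint is named with its own model, and its error rate is untouched. What remains is the reliability of the secondary significance statements.

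Three stronger readings are tempting, and the document does not support them.

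- **That the plan tests every outcome at every window.** The method table assigns methods by outcome. Testing by window is inferred from the period wording, which names three windows and chooses none.
- **That a false secondary result is close to certain.** That needs about 61–64 nearly independent tests. The windows are nested, and many outcomes overlap, such as oxygen use, respiratory rate, dyspnea and intensive care.
- **That an ineffective drug would show several significant benefits.** The roughly three expected false positives split between the arms, and several entries are not efficacy outcomes. The expected number of false benefits is 0.4 to 1.1 on the counts above.

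**Conclusion.** The point holds in a limited form. The protocol calls any p≤0.05 significant, unadjusted, across 21 secondary outcomes, 20 of them without a main window. If the drug affects none of them, the chance of at least one false significant result is about 66% with one test per outcome if independent, and about 43% at a between-outcome correlation of 0.5. If all windows are tested, it is about 55–94% over the assumed correlations and at most about 96% under independence. Even the lowest figure, 43%, is more than eight times the nominal 5%. About half of the false results would favour the drug. The correlations are assumptions, and splitting composite outcomes would raise the figures. This is a wording fault that should be corrected; it does not threaten the primary analysis.

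**What to change.** In section 11.3, with the synopsis aligned:

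- Limit the p≤0.05 significance statement to the prespecified analyses under the primary objective, that is, the efficacy model and the serious-adverse-event model given there.
- State that p-values for secondary outcomes are nominal. Report these outcomes as estimates with 95% confidence intervals and no significance claim.
- Name one main window for each secondary endpoint and show the others descriptively. D15 would match the primary endpoint. D28 is usable only after its definitions are reconciled: days after discharge in the synopsis and section 5.1.1, two weeks after the end of treatment in section 7, two weeks after discharge in section 7.3, and days after the start of treatment in Table 10. Note 3 to Table 10 also leaves the D28 examinations to the investigator, so that must be settled too. D21 is unsuitable because its procedures cover only those still in hospital.
- Optionally, add a short ordered list of key secondary endpoints.

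This is a text change with no extra participants or visits. The downside is that fewer results can be called significant.
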